#### 4.3.2. **AEs**

All AEs will be coded, using MedDRA dictionary version 17.0. The use of another version will not be considered a violation of the SAP, nor require an amendment to the plan. All summary tables will be based on coded preferred terms (PTs), instead of verbatim terms. The only exception being all rashes are combined into one category named RASHES. The categories and definitions of severity and causal relationship for all AEs, including the criteria for which an AE is to be classified as "serious," are as described in the protocol (Section 8).

A treatment-emergent AE (TEAE) is defined as any event not present before exposure to study drug or any event already present that worsens in either intensity or frequency following exposure to study drug. AEs with missing start dates, but with stop dates either overlapping into the dosing period or missing, will be considered TEAEs. A TEAE with missing severity or relationship will be considered severe or related, respectively.

The overall incidence of TEAEs will be summarized for all patients in the SAF Population. The number and percentage of patients having the following will be tabulated:

- TEAE
- Serious TEAE
- TEAE leading to discontinuation
- TEAE with outcome of death
- TEAE related to study drug (definitely, probably, or possibly)

- Severe TEAE
- Class C TEAE per the Centers for Disease Control and Prevention (CDC) Classification System for HIV Infection

The overall incidence of TEAEs will also be summarized by System Organ Class (SOC), and by SOC and PT. The number and percentage of patients reporting an event, as well as the number of events reported by the patients will be tabulated. The incidence of serious TEAEs and TEAEs leading to study discontinuation (if any) will be summarized in the same manner. If there are multiple occurrences of the same TEAE within any SOC or PT for the same patient, only the first occurrence will be counted.

The incidence of TEAEs by severity/grade (mild, moderate, severe, or potentially life-threatening) and by relationship to study drug (unrelated, possibly related, probably related, and definitely related), and the incidence of SAEs by relationship to study drug, will also be summarized.

All other AEs will be classified as non-TEAEs and identified in listings only. Serious TEAEs, TEAEs leading to study discontinuation, and TEAEs with an outcome of death will be presented in separate listings, if needed.

These tables will be repeated for patients receiving an investigational agent [Fostemsavir (BMS-068), Cabotegravir, or PRO140] as a concomitant medication versus those patients who did not receive an investigational agent.

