
Safety and Effectiveness Assessments:
	
Primary safety and effectiveness variables:
 
Cohort 1 and Cohort 2
 
 ■ Safety and tolerability of ibalizumab as assessed by AEs and Discontinuations 
Cohort 2 only
 
 ■ Proportion of patients achieving a $\geq 0.5 \log_{10}$ decrease from Baseline in viral load at Day 7 
Secondary safety and effectiveness variables:
 
Cohort 1 and Cohort 2
 
 ■ HIV-1 sensitivity/susceptibility changes associated with virologic failure after administration of ibalizumab 
Cohort 2 only
 
 ■ Proportion of patients with HIV-1 RNA levels < 50 copies/mL and < 400 copies/mL at assessment time points ■ Mean change from Baseline in viral load at Day 7 and all assessment time points ■ Proportion of patients achieving a $\geq 0.5 \log_{10}$ and $\geq 1.0 \log_{10}$ decrease from Baseline in viral load at all assessment time points

Safety Assessments:
	
Safety assessments will include the following:
 
 ■ Physical examinations ■ Vital sign measurements ■ Clinical laboratory parameters (hematology, serum chemistry, and urinalysis) ■ Monitoring of AEs and concomitant medications ■ Incidence of Class C events as defined by the CDC Classification System for HIV Infection (Appendix A) ■ Anti-ibalizumab antibody levels (immunogenicity of ibalizumab)

Statistical Considerations:	
Sample Size: A sample size of approximately 100 patients is anticipated to be enrolled, though the number of participating patients will not be limited and may exceed 100. The analysis of study data will be primarily descriptive, with emphasis on tabular and graphical displays. Summary descriptive statistics will be calculated along with point and interval estimates of AEs.
 
Effectiveness: (Cohort 2 only) The primary effectiveness endpoint of the study is the proportion of patients achieving a $\geq 0.5 \log_{10}$ decrease from Baseline in viral load at Day 7.
 
Safety Analyses: The safety analyses will include descriptions of treatment-emergent AEs (TEAEs), Class C events per the CDC Classification System for HIV Infection, clinical laboratory test results, physical examination findings, vital sign results, and immunogenicity of ibalizumab.

------------------------------------	---

ABBREVIATIONS

ABBREVIATION	TERM
AE	adverse event

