Eligible patients who are not participating in an Investigator-sponsored or TaiMed-sponsored ibalizumab IND (Cohort 2 of this study) will undergo a Screening period of, at most, 6 weeks. Patients will start treatment with ibalizumab 2,000 mg IV (loading) on Day 0 and then 800 mg IV (maintenance) on Day 14 and every 2 weeks thereafter. All patients will also receive an OBR beginning at Day 0. Treatment will continue until treatment-limiting toxicity, virologic failure, loss to

follow-up, withdrawal from the trial, pregnancy, discontinuation of ibalizumab development, or commercial availability of ibalizumab.

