9.7.1 Adverse Events

The incidence (n and %) of AEs, SAEs, and early termination of study medication or study participation due to an AE will be presented. Additionally, AEs will be tabulated according to severity and relatedness categories as reported by the investigator. AEs will be presented in tables organized alphabetically by Preferred Term within System Organ Class. Each patient will be counted only once for each AE reporting level.

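### TEAEs are summarized only as n, % and event counts although AE follow-up can run from about 4 to about 148 weeks; on-study exposure-adjusted rates should be added

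*SAP*

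**What the plan says.** The Protocol Summary lists as a primary variable for both cohorts "Safety and tolerability of ibalizumab as assessed by AEs and Discontinuations". Protocol 9.7.1 sets the measure: "The incidence (n and %) of AEs, SAEs, and early termination of study medication or study participation due to an AE will be presented". SAP 4.3.2 follows it: "The overall incidence of TEAEs will be summarized for all patients in the SAF Population". For the headline rows, "The number and percentage of patients having the following will be tabulated"; the System Organ Class and preferred-term tables give patients with an event "as well as the number of events reported by the patients will be tabulated", with repeats of the same TEAE in a patient counted once.

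The denominator is the SAF Population (SAP 3.2.2), which takes in anyone with one partial dose, however long they were observed. SAP 2.1 allows up to 144 weeks of treatment and a Week 150 visit. Protocol 8.3 collects AEs from first dose until 30 days after the last. Protocol 3.2 lists what ends treatment earlier, including "follow-up, withdrawal from the trial, pregnancy, discontinuation of ibalizumab development, or commercial availability of ibalizumab".

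SAP 3.4.1 displays results for TMB-301 rollovers, TMB-202 rollovers at each of two doses, Cohort 2, and the total. SAP 4.3.2 adds a second split: "These tables will be repeated for patients receiving an investigational agent [Fostemsavir (BMS-068), Cabotegravir, or PRO140] as a concomitant medication", set against those who did not receive one.

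SAP 4.3.1 summarizes cumulative dose and treatment duration separately. For Cohort 1 the duration starts at the first dose in the earlier study.

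**The concern.** The proportion of patients with at least one event rises with time watched, even when the underlying rate is constant. Here time watched varies between patients by design. Entry is not capped, patients can leave for individual reasons, and commercial availability is a calendar stop that falls at a different study week for each entry date. The plan then shows percentages side by side for several groups, and neither document gives a person-time rate, a time-to-first-event summary or a common time window for AEs.

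What is at stake is the descriptive reading of a primary variable. If one column was observed for less time than another, a lower percentage in it cannot be separated from a lower AE rate. The pooled total has a related problem: it averages over an unstated mixture of follow-up lengths. Event counts without person-time share the weakness.

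**Working it through.** No figure in the plan can be reproduced here; the sample size of about 100 has no derivation. The check is therefore of the range of follow-up, the effect on a crude percentage, and whether the exposure table could repair it.

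**1. Range of AE follow-up** (SAP 2.1 and 3.2.2, Protocol 8.3)
- Shortest while on study, one dose: 30/7 = 4.3 weeks.
- Longest, last dose at Week 144: 144 + 30/7 = 148.3 weeks.

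**2. Crude percentage against follow-up**

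Assume a constant first-event rate L per patient-year. After t weeks the expected crude percentage is 1 − exp(−L × t/52.18).

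With L = 0.3 (assumed):
- 24 weeks: 1 − exp(−0.138) = 12.9%
- 48 weeks: 24.1%
- 96 weeks: 42.4%
- 144 weeks: 1 − exp(−0.828) = 56.3%

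The ratio of last to first is 56.3/12.9 = 4.4, with no difference in rate.

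The table covers a range of rates. To have one rate of a scale seen in the documents, Protocol Table 1 gives diarrhea in 3 of 40 TMB-301 patients over 23 weeks: L = −ln(1 − 3/40)/23 × 52.18 = 0.177 per patient-year. The other rates are assumed.

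| Rate per patient-year | 4.3 wk | 24 wk | 48 wk | 96 wk | 148.3 wk |
|---|---|---|---|---|---|
| 0.05 | 0.4% | 2.3% | 4.5% | 8.8% | 13.2% |
| 0.10 | 0.8% | 4.5% | 8.8% | 16.8% | 24.7% |
| 0.177 | 1.4% | 7.8% | 15.0% | 27.8% | 39.5% |
| 0.25 | 2.0% | 10.9% | 20.5% | 36.9% | 50.9% |
| 0.50 | 4.0% | 20.5% | 36.9% | 60.1% | 75.9% |
| 2.00 | 15.1% | 60.1% | 84.1% | 97.5% | 99.7% |

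The last row stands for a very common outcome such as any TEAE. Beyond about a year it is close to its ceiling, so differences in follow-up matter little there. In the lower-rate rows the percentage keeps climbing.

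**3. Order can reverse.** At 0.50 per patient-year and 48 weeks the crude figure is 36.9%. At half that rate, 0.25, and 144 weeks it is 49.8%.

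**4. Rate per person-time.** Expected patient-years to first event or end of follow-up are (1 − exp(−Lt))/L, with t in years. Dividing the crude proportion by this gives L at every t. At L = 0.10 the result is 10.0 per 100 patient-years at 24, 48, 96 and 148.3 weeks, while the crude figure goes from 4.5% to 24.7%.

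**5. Can SAP 4.3.1 supply the denominator?** Not for Cohort 1, because it counts prior-study time while the events of interest occur in TMB-311. As an assumed illustration, 24 prior weeks (the gap between the Week 174 and Week 150 in the footnote to SAP Listing 16.2.6.2) would scale the rate by 48/(48 + 24) = 0.67 for a patient with 48 on-study weeks, or by 150/174 = 0.86 for one with 150.

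**6. Numerator and denominator must share a window.** The TEAE definition in SAP 4.3.2 has no end date. AEs are also recorded at Week 150, six weeks after a Week 144 dose, while Protocol 8.3 stops at 30 days. An event between those points would be counted with no time at risk unless the window is fixed for both.

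**The case against.** The study is single-arm in purpose, open-label and descriptive; SAP 3.4.2 plans no formal hypothesis test, and no between-group safety claim is announced. Reporting n and % is ordinary practice in expanded access. Exposure is tabulated in the same groupings, so a reader is not blind to it. All of this stands. It limits the point to how descriptive tables are read, and no type I error rate is affected. The exposure table is only a partial answer, because it is not tied to AEs and runs on a different clock for Cohort 1.

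A reader might infer that groups with shorter follow-up will in fact look safer. The documents do not support that: they give no entry dates, accrual period or follow-up by group, and the commercial-availability stop applies to every cohort.

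A reader might also infer that adjusted rates would make Cohorts 1 and 2 comparable, or restore comparison with TMB-301. Neither follows. Cohort 1 patients were already receiving ibalizumab and had passed their early exposure before entry, whereas Cohort 2 patients are ibalizumab-naive. Protocol Table 1 reports adverse reactions at a 5% threshold over 23 weeks, a different event definition, and neither document plans that comparison.

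Finally, a single rate assumes roughly constant risk. Protocol 4.2 notes first-dose rash with therapeutic antibodies. For events that cluster early, long follow-up dilutes the rate, so the rate alone can also mislead. That objection stands and shapes the fix.

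**Conclusion.** The concern holds as a conditional one. The plan reports a primary variable as percentages and counts only, while individual AE follow-up can differ by a factor of about 35 (148.3/4.3). If average follow-up differs between displayed groups, serious, discontinuation, Class C and single-preferred-term rows will reflect observation time as well as AE rate. The any-TEAE row is less affected once follow-up is moderate.

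The size in this trial is unknown. The 13% against 56% illustration rests on an assumed constant rate of 0.3 per patient-year and on comparing whole groups at 24 and 144 weeks; a smaller gap in follow-up gives a smaller distortion, and equal follow-up gives none between groups. This is a worthwhile addition to the tables rather than a flaw that invalidates them.

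**What to change.** In SAP 4.3.2, keep n and % and add:

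- **Rates.** Patients with a first event per 100 patient-years, with a 95% CI, for the headline rows and common preferred terms, by displayed group.
- **One window for both parts.** Count events with onset from the first TMB-311 dose to 30 days after the last TMB-311 dose. Count person-time over the same window, ending at first event or exit if earlier. State that this clock differs from the one in SAP 4.3.1.
- **Early-window table.** For events that may cluster after first infusions, n and % within a common early period, for example the first 24 weeks on study. Note that for Cohort 1 this is not the first period on ibalizumab.
- **A caution in the text.** Results are descriptive, and Cohorts 1 and 2 differ in how patients were selected whichever measure is used.

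The cost is a few table columns and one short table, programmed from AE onset and infusion dates already collected. Study conduct does not change. The remaining weakness is the constant-risk assumption behind each rate, which the early-window table helps the reader to judge.

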5.3 Patient Withdrawal and Discontinuation

5.3.1 Reasons for Withdrawal

A patient may be withdrawn from the study if the patient:

- Withdraws consent to participate or requests an early discontinuation at any time during the study
- Is in violation of the protocol
- Becomes pregnant during the study (see [Section 8.7](#) for a description of procedures to be followed in case of pregnancy)
- Experiences virologic failure
- Experiences a treatment-related serious or intolerable AE(s) (according to DAIDS criteria, see Appendix B)
- Experiences toxicity, defined as two consecutive laboratory results, at least 14 days apart, with a CD4⁺ cell count below 200 cells/mm³ that also represents a 50% reduction from the baseline CD4⁺ cell count

The study treatment should be discontinued for all Grade 3 or 4 treatment-related abnormalities, as defined in Appendix B. Treatment-emergent Grade 3 or Grade 4 lab abnormalities should be retested within 72 hours. Any patient with a Grade 3 or Grade 4 lab abnormality that resolves before the next scheduled dose may have the study drug reinstated. If a patient develops a persistent Grade 3 or Grade 4 treatment-emergent laboratory abnormality, excluding triglycerides and cholesterol, that does not resolve prior to the next scheduled study drug administration, study drug may be discontinued.

A patient experiencing one or more treatment-emergent SAEs will receive treatment and follow-up evaluations by the Principal Investigator, or they will be referred to another appropriate physician for treatment and follow-up. Withdrawal from the study will be at the discretion of the Principal Investigator/Sponsor.

The investigator will also withdraw a patient if the Sponsor or local regulatory agency (e.g., FDA) terminates the study. Upon occurrence of an SAE, the Principal Investigator will notify the Sponsor or designee of these events via the SAE hotline. If a patient is discontinued because of an AE, the

event will be followed until satisfactory resolution or until the Principal Investigator deems the event to be chronic or the patient to be stable.

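### SAP 4.3.2 names by term only the TEAEs that lead to study discontinuation, while protocol 9.7.1 also covers AEs that end study medication, and the SAP overview row is undefined

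*SAP*

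**What the plan says.** The Protocol Summary gives the primary safety variable for both cohorts as "Safety and tolerability of ibalizumab as assessed by AEs and Discontinuations". It does not say whether discontinuation means study drug, study participation, or both. Protocol 9.7.1 does: "The incidence (n and %) of AEs, SAEs, and early termination of study medication or study participation due to an AE will be presented". The same section sets the general layout of the AE tables: "AEs will be presented in tables organized alphabetically by Preferred Term within System Organ Class".

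SAP 4.3.2 has three outputs on this topic, all in the SAF Population:

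- an overview row, "TEAE leading to discontinuation", with no statement of what is discontinued;
- a table by System Organ Class and Preferred Term: "The incidence of serious TEAEs and TEAEs leading to study discontinuation (if any) will be summarized in the same manner";
- separate listings: "Serious TEAEs, TEAEs leading to study discontinuation, and TEAEs with an outcome of death will be presented in separate listings, if needed".

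SAP 4.1 and protocol 9.3 treat premature discontinuation of study medication and premature discontinuation of the study as separate outcomes. Both tabulate a primary reason, and any additional reasons for stopping study medication.

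**The concern.** The protocol's measure has two parts, and the two SAP outputs that link events to discontinuation by name carry only one of them. The SAP gives no reason for the narrowing. *Study discontinuation* cannot comfortably be read as including drug stops, because the SAP's own disposition section keeps the two apart. A programmer following the SAP's vocabulary would leave drug-only stops out of both outputs.

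This is an open-label, single-arm-type program with no formal hypothesis testing planned (SAP 3.4.2), so descriptive tables and listings carry the tolerability evidence. A reader who asks which events ended ibalizumab would turn to the by-term table and the listing, and could get an incomplete answer without knowing it.

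**Working it through.** No arithmetic decides this point and the plan gives no figure to reproduce. The check compares wording and then follows individual cases through the outputs.

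**Step 1. What each output covers**

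| Output | Study drug stopped for an AE | Study left for an AE | Event named |
|---|---|---|---|
| Protocol 9.7.1 incidence | yes | yes | by-term layout is stated for AEs generally, not for this measure |
| SAP 4.3.2 overview row | undefined | yes | no |
| SAP 4.3.2 by-term table | no | yes | yes |
| SAP 4.3.2 separate listing | no | yes | yes |
| SAP 4.1 disposition | yes, if AE is a reason category | yes, on the same condition | no |

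No output is clearly defined as the protocol's two-part measure.

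**Step 2. Whether the excluded cases can arise**

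- Protocol 5.3.1 says "The study treatment should be discontinued for all Grade 3 or 4 treatment-related abnormalities". It separately leaves study withdrawal after a serious AE to the discretion of the investigator or sponsor. Stopping drug and leaving the study are therefore distinct acts.
- Under protocol 4.4.2, a Cohort 2 patient with more than 28 days without an infusion is withdrawn. If the gap began with an AE, the recorded exit reason could be missed doses.
- Under protocol 4.4.1, a Cohort 1 patient with a long gap (more than 28 days at 800 mg, more than 42 days at 2,000 mg) may be withdrawn, so exit is not automatic.

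**Step 3. Following cases through the SAP**

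- *An AE stops drug and is the recorded reason for leaving the study.* The case appears in every output.
- *An AE stops drug; study exit is recorded as missed doses or withdrawn consent.* It is absent from the by-term table and the listing. Its place in the overview row depends on how the row is read. It should be counted in disposition as a medication stop, through the primary or additional reasons.
- *An AE stops drug and the patient does not leave the study.* The result is the same, with no study exit to record.
- *Drug is interrupted and later reinstated, as 5.3.1 allows.* This is an interruption, not an early termination, and falls outside the measure in both documents.

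The gap lies in the second and third cases.

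**Step 4. Size**

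The documents do not report how many patients fall into those two cases. With the anticipated enrollment of about 100 (SAP 3.1), one omitted patient is 1/100 = 1 percentage point of the total.

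Protocol 1.2 reports one treatment-related TEAE leading to study discontinuation in the Phase 2b trial of 113 patients (1/113 = 0.9%). That figure cannot serve as a base rate: it is limited to treatment-related events, concerns leaving the study rather than stopping drug, and comes from a trial whose results are described at Week 24, whereas this study runs up to 144 weeks.

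**The case against.** A reader might infer that AE-driven drug stops are lost from a primary tolerability variable, or that ibalizumab will be shown as better tolerated than it is. The documents do not support either reading. SAP 4.1 tabulates premature stopping of study medication with primary and additional reasons. The overview row is ambiguous rather than restrictive and can include drug stops. Every TEAE still enters the tables by System Organ Class and Preferred Term, by severity and by relationship. What may be missing is the link between a named event and a drug stop.

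It is also fair to say that protocol 9.7.1 asks for an incidence and does not expressly require a by-term table or listing of discontinuation AEs. A clearly defined overview row together with disposition could satisfy it. Lasting drug-only stops are probably uncommon: protocol 3.1 has patients discontinued from the study for treatment-related serious or intolerable AEs, 4.2 couples drug discontinuation with withdrawal for related anaphylactoid symptoms, 4.4.2 withdraws Cohort 2 patients after long gaps, and no continuing off-drug visit schedule is described beyond the Early Withdrawal and Week 150 visits. The AE table and listing shells are not in the available text, so they may already resolve part of this.

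These arguments limit the consequence but do not remove the mismatch. Disposition gives reasons, not event terms. It summarizes all enrolled patients, whereas the AE tables use the SAF Population, so denominators can differ. SAP 4.3.2 repeats its AE tables by use of an investigational agent, and SAP 4.1 states no such repeat. Once the SAP provides a by-term table and a listing of discontinuation events, they should follow the protocol's concept or say why they do not.

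**Conclusion.** The point holds as an unexplained narrowing. The by-term table and listing in SAP 4.3.2 cover less than the measure in protocol 9.7.1, and the overview row is undefined. AEs that ended study drug without being the recorded reason for leaving the study would not be identified in the outputs that name discontinuation events.

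The effect is on completeness of description. Total TEAE counts are unaffected, and the number of AE-driven drug stops should remain visible in disposition. That last statement assumes AE is one of the reason categories, which the text does not list. The number of patients involved is unknown and probably small. The documents do not establish that tolerability would be misrepresented, and nothing here questions any clinical stopping rule. It is a modest correction worth making before the AE outputs are programmed.

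**What to change.** In SAP 4.3.2:

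1. Define the overview row as *TEAE leading to discontinuation of study drug or of the study*, with sub-rows for study drug and for study. A patient may count in both sub-rows but only once in the combined row.
2. Use the same definition for the table by System Organ Class and Preferred Term and for the separate listing. Show in the listing which component applies.
3. State how cases are identified: from the recorded primary and additional reasons for stopping study medication, linked to the AE record.

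On step 3 the sponsor should confirm whether an action-taken field exists for non-serious AEs. Protocol 8.3 does not list one among the AE data items; protocol 8.6 mentions suspension or discontinuation of study drug only for SAE reports. Without such a field, linking a drug stop to a specific event may need manual reconciliation.

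The cost is SAP wording, two sub-rows and minor programming, plus any reconciliation. The reported discontinuation count may come out slightly higher.

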8.5 Assessment of Severity

The intensity of the AE will be rated by the investigator as mild, moderate, severe, or potentially life-threatening using the following criteria:

Mild (Grade 1): Symptoms causing no or minimal interference with usual social and functional activities.

Moderate (Grade 2): Symptoms causing greater than minimal interference with usual social and functional activities.

Severe (Grade 3): Symptoms causing inability to perform usual social and functional activities.

Potentially Life-Threatening (Grade 4): Symptoms causing inability to perform basic self-care functions OR medical or operative intervention indicated to prevent permanent impairment, persistent disability, or death.

Details for grading severity are given in Appendix B. Changes in the severity of an AE should be documented to allow an assessment of the duration of the event at each level of intensity to be performed. AEs characterized as intermittent require documentation of onset and duration of each episode.

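### The first-occurrence rule in SAP 4.3.2 reduces the planned PT-level event counts to patient counts, and the available text does not say which episode supplies the grade or relationship

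*SAP*

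**What the plan says.** SAP 4.3.2 sets out the SOC and SOC/PT tables in one paragraph. On their content: "The number and percentage of patients reporting an event, as well as the number of events reported by the patients will be tabulated". On two further sets of tables: "The incidence of serious TEAEs and TEAEs leading to study discontinuation (if any) will be summarized in the same manner". The paragraph closes with the counting rule: "If there are multiple occurrences of the same TEAE within any SOC or PT for the same patient, only the first occurrence will be counted". All rash terms are pooled into a single category, and the AE tables are repeated by use of an investigational background agent.

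The next paragraph plans "The incidence of TEAEs by severity/grade (mild, moderate, severe, or potentially life-threatening" and also "by relationship to study drug (unrelated, possibly related, probably related, and definitely related". It does not say which of several episodes represents the patient. The one worst-case convention in the section deals with missing values only: "A TEAE with missing severity or relationship will be considered severe or related, respectively".

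Protocol 9.7.1 also plans tabulation by severity and relatedness. It counts a patient once at each reporting level but names no episode. On data collection, Protocol 8.5 says: "Changes in the severity of an AE should be documented". It also asks for the onset and duration of each episode of an intermittent event.

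**The concern.** The paragraph promises a count of events and two sentences later discards every repeat. Both instructions cannot be followed in the same event column. A programmer who applies the rule literally produces an event column that carries no information beyond the patient column.

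The severity and relatedness tables have a related gap. Counting a patient once means choosing an episode, and first occurrence is the only choice that the available text names anywhere. If it were borrowed for these tables, any error could run in one direction only, because the first episode can never be worse than the worst one.

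Adverse events are a primary safety variable in both cohorts, and treatment can last up to 144 weeks. The TEAE definition itself includes worsening in intensity or frequency, so recurrence and escalation are among the things these tables should show. Pooling all rashes makes repeats of one term more likely, since different rash terms in the same patient become occurrences of a single category.

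**Working it through.** The plan states no figure to reproduce. The study is descriptive, and neither document gives a recurrence rate or a per-episode grade distribution. The first step below is a reading of the text; the numerical inputs in the later steps are assumptions.

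**1. Event column, literal reading.** Let n be the patients with a given PT and m the mean number of episodes per affected patient. True events = n × m. Events under the rule = n. Undercount = (nm − n)/(nm) = 1 − 1/m.

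With n = 20 (assumed):

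| m | true events | events shown | undercount |
|---|---|---|---|
| 1 | 20 | 20 | 0% |
| 1.25 | 25 | 20 | 20% |
| 1.5 | 30 | 20 | 33% |
| 2 | 40 | 20 | 50% |
| 3 | 60 | 20 | 67% |

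The percentage does not depend on n.

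**2. One patient (assumed).** The first episode of a PT is Grade 1 and unrelated; a later episode of the same PT is Grade 3 and probably related.
- First occurrence applied throughout: 1 patient, 1 event, mild, unrelated.
- All events, worst episode: 1 patient, 2 events, severe, probably related.

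**3. Severity table, only if first occurrence is carried over to it.** Let p be the chance that an episode is Grade 3 or higher and k the number of episodes. If episodes are independent, the chance that a patient has at least one such episode is 1 − (1 − p)^k, while first occurrence shows p. The share of these patients missed at PT level is 1 − p/[1 − (1 − p)^k].

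- p = 0.10, k = 3: 1 − 0.9³ = 27.1%, against 10% shown; 63% missed.
- p = 0.10, k = 5: 1 − 0.9⁵ = 41.0%, against 10% shown; 76% missed.
- Over p = 0.05 to 0.20 and k = 2 to 5, the share missed runs from 44% (p = 0.20, k = 2) to 78% (p = 0.05, k = 5). With k = 1 it is zero.

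Independence enlarges the gap. Under a beta-binomial with p = 0.10 and within-patient correlation 0.5 (parameters 0.1 and 0.9), the chance of no Grade 3+ episode is:
- k = 3: (0.9/1)(1.9/2)(2.9/3) = 0.827, so 17% have at least one;
- k = 5: 0.827 × (3.9/4)(4.9/5) = 0.790, so 21% have at least one.

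The gap to the 10% shown is then 7 and 11 percentage points, rather than 17 and 31.

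**4. What the overall rows still catch.** The summary list in SAP 4.3.2 counts patients having a severe TEAE and patients having a related TEAE. These are any-event counts, listed before the first-occurrence sentence. The patient in step 2 appears in both rows, whatever happens in the PT breakdown.

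**The case against.** The best defence is that the sentence was meant for patient counts only, where counting each patient once is ordinary practice. That may well be the intention, but the sentence does not say so, and it closes a paragraph that promises event counts.

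On severity and relatedness the defence is stronger. The first-occurrence sentence belongs to the SOC/PT paragraph, and the severity and relationship tables come in the next one, without it. Protocol 9.7.1 can be read as counting a patient once within each severity category, which would place the step 2 patient under both mild and severe. No AE table shell is available in the public copy of the SAP. Other shells in it carry definitions in footnotes, so a maximum-severity footnote cannot be excluded. All of this stands.

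A reader might therefore infer too much in three ways:
- **That a patient with a mild first episode and a severe later one is tabulated as mild.** The documents do not say this; they leave the choice of episode open.
- **That escalation is hidden altogether.** The overall rows for severe and related TEAEs would still include the patient. A later serious episode still places the patient in the serious-TEAE table, and separate listings are planned, if needed, for serious events, discontinuations and deaths.
- **That Grade 4 events disappear.** They keep their own category in the severity table. Only the label of the summary row is open to a narrow reading, because Protocol 8.5 treats severe and potentially life-threatening as separate grades.

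It is also fair to say that the study is descriptive and that sites record each intermittent episode and changes in severity. Nothing is lost from the data.

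**Conclusion.** The event-count conflict is established from the text alone. The stated rule makes PT-level event counts equal patient counts, and this carries into the serious-TEAE and discontinuation tables and the repeats by investigational-agent use. Its size is 1 − 1/m. This is nil where nobody has a repeat and one half at two episodes per affected patient; the documents do not allow m to be estimated.

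The severity and relatedness part is a gap in specification, not a demonstrated error. The available text does not name the episode that supplies the grade or relationship. If first occurrence were used, the loss would be confined to the PT-level breakdown and would always favour a milder profile. The percentages for that case rest on assumed rates and fall markedly once episodes within a patient are correlated, so they illustrate direction rather than expected size.

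The wording should be settled before the AE tables are programmed, because adverse events are a primary variable. It does not threaten the collected data.

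**What to change.** Replace the first-occurrence sentence in SAP 4.3.2 with:

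*For patient counts, each patient is counted once per SOC and PT; in the severity and relationship tables the patient is counted at the highest severity and strongest relationship across all occurrences; event counts include all occurrences.*

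Relabel the summary row for severe TEAEs as *Severe or potentially life-threatening (Grade 3 or 4) TEAE*, so that it cannot be read as leaving out Grade 4.

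The cost is one sentence, one row label and a sort by worst grade and strongest relationship in the table programs. The data are already collected under Protocol 8.5, and the patient count agrees with Protocol 9.7.1. If a table footnote already sets a worst-episode rule, the edit simply brings the SAP text into line with it.
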